## Test Hypothesis and Verification

Null hypothesis (H0 ): The high-risk HPV test results of the samples collected by physicians and those collected by subjects themselves were consistent with Cohen 's kappa coefficient  $k \leq 0.66$ .

Alternative Hypothesis (H1 ): The high-risk HPV test results of the samples collected by the physician and the samples collected by the subjects themselves are consistent with Cohen 's kappa coefficient  $k > 0.66$ .

If the test results show that the opposite hypothesis is established, the expected goal of the test is achieved.

## Sample size calculation

The above-mentioned kappa value is preset to be 0.72, under the condition that the test power is 80% and the significance level is 0.05, according to the proportion of subjects included in each group, the required samples are 1,049 cases . Considering that there are up to 10% of invalid samples and patients requesting to withdraw from the trial, the trial is expected to recruit 1,200 subjects , and the number of subjects assigned to each group is as follows according to the original test group ratio.

5 groups of subjects included in the subjects	Inclusion ratio	Estimated number of people included
1. No history of abnormal smear or cervical lesions	10%	120 people
2. There have been mild smears or pathological abnormalities within 3-12 months, and those who need to receive Pap smear follow-up	15%	180 people
3. Those who have had moderate to severe smear or pathological abnormalities or cervical cancer, have received conical surgery, and are currently receiving follow-up	20 %	240 people
4. Mild smears or pathological tissue abnormalities within 3 months, who have not yet been treated	20 %	240 people
5. Moderate and severe abnormalities in smear or pathological tissue or cervical cancer found within 3 months, and those who have not received treatment	35%	420 people
The total number of subjects expected to be included		1,200 people

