- (2) The high-risk HPV test results are inconsistent (disagreement). One of the samples collected by the doctor or self-collected does not have any of the above-mentioned high-risk HPV types, and the other has any of the above-mentioned high-risk types.
- 2. The consistency between the test results of the specimens collected by the physician and the specimens collected by the subjects will be evaluated by Cohen 's kappa coefficient or related test comparisons.
- C. The consistency assessment will use valid samples as the analysis group, that is, the samples collected by the verification physician and the self-collected specimens of the same subject are both valid samples. Valid specimens are defined as those who test positive for the  $\beta$ -globin gene in the internal control group of the [name] Papillomavirus Genotyping Test Kit.
- D. Safety, self-sampling success rate, and satisfaction evaluation are based on the intent-to-treat population (ITT).

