## **Outcome measures**

### **Primary evaluation indicators:**

- A. HPV16, 18, 31, 33, 35, 39, 45, 51, 52, 56, 58, 59, 66, 68 and other 14 types are high-risk cancer-causing types. Therefore, the main purpose of the agreement is whether there is high-risk HPV detected in the samples collected by doctors and self - sampled . Consistency is defined as follows:
- B. The high-risk HPV test results are consistent (agree) , and the test results show that both of them have any of the above-mentioned high-risk HPV or neither of them has high-risk HPV .
- C. The test results of high-risk HPV are inconsistent ( disagree ). One of the samples collected by doctors and self- collected samples does not have any of the above-mentioned high-risk HPV types , and the other has any of the above-mentioned high-risk types.
- D. The consistency between the test results of the samples collected by the physician and the test results of the subjects' self- collected samples will be evaluated by Cohen 's kappa coefficient or compared with related tests.

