agreement (chance agreement). The standard error of the Kappa statistic is based on Fleiss, Cohen, and Everitt (1969) as  $SE(K) = SD(K)/\sqrt{N}$ , where  $SD(K) = \sqrt{P_0(1 - P_0)/(1 - P_c)^2}$ . The 100(1- $\alpha$ )% interval estimate of the Kappa statistic is  $K \pm z_{\alpha/2} SE(K)$ .

		Physician check		sum
		High-risk HPV detected	No high-risk HPV detected	
self - test	High-risk HPV detected	a	b	rm1
	No high-risk HPV detected	c	d	rm2
	sum	cm1	cm2	no

For each HPV type ( type-specific) , the consistency between the test results of the samples collected by the physician and the samples collected by the subjects will be evaluated by Cohen 's kappa coefficient or compared with related tests.

- G. Consistency assessment will take valid samples as the analysis group, that is, the same subject's verification physician and self- sampling samples are all valid samples.
- H. A valid sample is defined as a positive test for the  $\beta$ -globin gene in the internal control group of Jingyu Human Papillomavirus Genotyping Detection Kit . The intent-to-treat group (ITT) was used as the analysis group for safety, self- collection success rate, and satisfaction evaluation.

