Reactive changes: Inflammation, repair, radiation, and others												
Atrophy with inflammation												
Atypical squamous cells (ASCUS)												
Atypical glandular cells												
Mild dysplasia (CIN1) with koilocytes												
Mild dysplasia (CIN1) without koilocytes												
Moderate dysplasia (CIN2)												
Severe dysplasia (CIN3)												
Carcinoma in situ (CIN3)												
Squamous cell carcinoma												
Adenocarcinoma												
Other malignant neoplasm												
Other												
Atypical glandular cells favor neoplasm												
Atypical squamous cells cannot exclude HSIL												
Dysplasia cannot exclude HSIL												
Endocervical adenocarcinoma in situ												

Table 4 Consistency of high-risk HPV detection in all cases

Physician-collected		Kappa statistic (95% CI)	p value	Overall Agreement
Self-collected	Positive	Negative		
Positive				
Negative				

High-risk HPV types include 16, 18, 31, 33, 35, 39, 45, 51, 52, 56, 58, 59, 66, 68 and other 14 types. The definition of consistency is as follows: high-risk HPV test results are concordant (concordant), the test results of the subject's physician -collected sample and self- collected sample both have any of the above-mentioned high-risk HPV (high-risk HPV positive) or both have no high-risk HPV (high-risk HPV negative); high-risk HPV test results are inconsistent (discordant), the test results of the subject's doctor-collected sample and self-collected sample, one does not have any high-risk HPV, and the other has any of the above- mentioned high -risk types .

Table 5 Consistency of high-risk HPV types detected in each group

Self-collected	Physician-collected		Kappa statistic (95% CI)	p value	Overall Agreement
	Positive	Negative			
Group 1					
Positive					
Negative					
Group 2					
Positive					
Negative					
Group 3					
Positive					
Negative					
Group 4					
Positive					
Negative					
Group 5					
Positive					
Negative					

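### Does the SAP leave open whether success on kappa is judged by a one-sided 0.05 test or by the two-sided 95% confidence limit?

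*SAP*

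**What the plan says.** - **Hypotheses** (SAP, Test Hypothesis and Verification): H0 is kappa ≤ 0.66 and H1 is kappa > 0.66 for high-risk HPV detection in the two specimens. Success is defined by H1: "If the test results show that the opposite hypothesis is established, the expected goal of the test is achieved".
- **Sample size** (SAP, Sample size calculation): true kappa 0.72, "under the condition that the test power is 80% and the significance level is 0.05", 1,049 cases needed. Recruitment is set at 1,200 to allow for up to 10% invalid samples and withdrawals.
- **Statistic** (SAP, Statistical design, methods and analysis procedures, item F): kappa is named as the statistic for verifying the result. Its standard error is given as SE = SD/√N, with SD = √[P0(1 − P0)/(1 − Pc)²]. The 100(1 − α)% "interval estimate of the Kappa statistic is" K ± z(α/2)·SE(K).
- **Output** (SAP, Table 4): a column "Kappa statistic (95% CI"), a p value whose null is not named, and overall agreement.
- **General endpoint wording**: agreement "will be evaluated by Cohen 's kappa coefficient or compared with related tests" (SAP, Primary evaluation indicators, item D). The Protocol has "will be evaluated by Cohen 's kappa coefficient or related test comparisons" (Statistical methods, item B.2).

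**The concern.** The level of 0.05 carries no label for sides. The only inferential formula written out for kappa uses z(α/2), which at α = 0.05 is the 95% interval of Table 4. Requiring its lower limit to exceed 0.66 is a one-sided test at 0.025, whereas the sample size uses 0.05. Neither document states a critical value or a confidence-limit rule, and the endpoint sections also admit unspecified related tests.

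This is the primary criterion of a trial meant to support device registration. At n = 1,049 an observed kappa between about 0.699 and 0.706 would pass one rule and fail the other. Table 4 could then report success beside a 95% interval that contains 0.66. If the interval decided, the trial would fall short of its stated power. If nothing decided, the rule could be picked after unblinding.

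**Working it through.** **Inputs.** Null kappa 0.66, true kappa 0.72, power 80% and level 0.05 come from the SAP. Overall positivity is 0.1×0.1 + 0.15×0.7 + 0.2×0.5 + 0.2×0.7 + 0.35×0.9 = 0.67, as the SAP states. Assumption: both sampling methods have positivity 0.67, since the documents give one overall rate.

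**Chance and observed agreement.**
- Pc = 0.67² + 0.33² = 0.5578, so 1 − Pc = 0.4422.
- P0 = Pc + kappa × (1 − Pc) = 0.8497 at kappa 0.66 and 0.8762 at kappa 0.72.

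**SD of kappa, two ways.**
- Formula printed in item F: √(0.8497 × 0.1503)/0.4422 = 0.8083 at 0.66, and √(0.8762 × 0.1238)/0.4422 = 0.7448 at 0.72.
- Full large-sample (Fleiss–Cohen–Everitt) variance: SD = √(A + B − C)/(1 − Pc)². With the cells a, b, c, d of the SAP's 2×2 table as proportions, r1, r2 its row margins and c1, c2 its column margins:
  - A = a[(1 − Pc) − (r1 + c1)(1 − P0)]² + d[(1 − Pc) − (r2 + c2)(1 − P0)]²
  - B = (1 − P0)²[b(c1 + r2)² + c(c2 + r1)²]
  - C = (P0·Pc − 2Pc + P0)²
  - Result: 0.8019 at 0.66 and 0.7410 at 0.72.

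**Reproducing 1,049.** n = [(z·SD(0.66) + 0.8416·SD(0.72))/0.06]².

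| Level | Full variance | Item F formula |
|---|---|---|
| One-sided 0.05, z = 1.645 | 1,048.2, so **1,049** | 1,063.1, so 1,064 |
| Two-sided 0.05, z = 1.96 | 1,338.7, so 1,339 | 1,358.0 |

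The one-sided level with the full variance matches exactly, and the printed SD comes within 3%. Using the variance at 0.72 alone with z = 1.96 gives 1,198 or 1,210, which does not match.

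**Power at n = 1,049, kappa 0.72.** Power = Φ[(0.06√n − z·SD(0.66))/SD(0.72)], full variance.
- z = 1.645: (1.9433 − 1.3190)/0.7410 = 0.8425, so 80.0%.
- z = 1.96: (1.9433 − 1.5717)/0.7410 = 0.5015, so 69.2%. With the variance at 0.72 only (Wald), 0.06√n/SD(0.72) − 1.96 = 0.66, so 74.6%.
- The item F formula gives 79.5%, 68.5% and 74.2% respectively.

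**Simulation** (400,000 tables per setting, SE from item F).

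| True kappa | Evaluable n | One-sided 0.05 succeeds | 95% lower limit > 0.66 | Rules disagree |
|---|---|---|---|---|
| 0.72 | 1,049 | 81.8% | 72.8% | 9.0% |
| 0.72 | 1,080 (1,200 less 10%) | 82.8% | 73.9% | 8.9% |
| 0.72 | 1,200 | 85.9% | 78.0% | 7.9% |
| 0.66 | 1,049 | 5.5% | 2.9% | 2.6% |

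At n = 1,049 disagreement is 11.8% at kappa 0.70, 3.1% at 0.74, 1.4% at 0.75 and under 0.1% at 0.78.

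**What the documents make of each rule.** A directional H1 at level 0.05, tested with the stated kappa and its SE, means rejecting H0 when (K − 0.66)/SE(K) > 1.645. That equals asking that the lower limit of the SAP's own interval formula, taken at 90%, exceed 0.66. The 95% interval appears as an estimate in item F and as a table column. The same interval and p value columns recur in Tables 5 to 7, which carry no success criterion, so they are a reporting format.

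**The case for a change.** The strongest case for a change is that a directional H1 does not settle the level: a one-sided claim can be judged at 0.05 or, through a 95% limit, at 0.025. The SAP writes out only the interval that goes with the second, and a reader of Table 4 would naturally compare 0.66 with the interval shown. One sentence would remove the doubt at no cost to recruitment or data.

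Part of this stands. The SAP does not label 0.05 as one-sided, does not name 0.66 as the null for the Table 4 p value, and does not call the 95% interval descriptive. The sizing formula is not printed either, and the exact match depends on 67% positivity: at 50%, which is not the SAP's input, a two-sided calculation with the variance at 0.72 alone would give about 1,050.

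The rest does not stand. The stated level is 0.05, not 0.025, and the stated sample size fits a one-sided 0.05 test. The loss of power arises only under a rule that the SAP never adopts. A two-sided 95% interval printed beside a one-sided 0.05 test does not contradict it. The wording about related tests is general: item F and the hypotheses then fix kappa, its SE and the bound of 0.66 for the primary endpoint. A Table 4 p value against any other null would not address those hypotheses.

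**Conclusion.** No change is needed. Read together, the directional hypotheses, the 0.05 level, the named statistic with its SE, and the 1,049 cases give one coherent rule: a one-sided 0.05 test of kappa against 0.66. Under it the stated 80% power is right (80.0% by formula, 81.8% simulated at 1,049, and 82.8% at the 1,080 left after a 10% loss), and simulated false success at kappa 0.66 is 5.5%, close to nominal.

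The alternative rule would lower power at kappa 0.72 to about 69–75% at 1,049, about 70–76% at 1,080 and about 78% (simulated) at 1,200. Its practical reach is a window of 0.007 in observed kappa at n = 1,049. What is missing is a label for sidedness and for one table column, which the SAP's own hypotheses and sample size supply. The conclusion rests on 67% positivity in both specimens and on large-sample behaviour of kappa.

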## Interim analysis

This trial had no interim analysis

## Secondary evaluation indicators to be analyzed

- A. Evaluation of the success rate (proportion of effective specimens) of HPV typing by doctors ' samples and self- collected samples of all detectable HPV types.
- B. Consistency assessment will take valid samples as the analysis group, that is, the same subject's verification physician and self- sampling samples are all valid samples. A valid sample is defined as a positive test for the  $\beta$  -globin gene in the internal control group of Jingyu Human Papillomavirus Genotyping Detection Kit . The intent-to-treat group (ITT) was used as the analysis group for safety, self- collection success rate, and satisfaction evaluation.
- C. used as a safety evaluation index to evaluate whether there will be adverse reactions (such as psychological discomfort or other physical discomforts) in the self - examination of vaginal secretions by doctors or by women .
- D. Evaluate whether women can complete effective self-specimen sampling by following the instructions or videos. The beta-globin of the test results will be used as an evaluation index for valid specimens, and the reliability of the explanatory files will be evaluated by the results of the questionnaire survey.

- E. -collection success rate (proportion of effective specimens) and consistency evaluation of each group under the test group .
- F. The correlation between the HPV test results collected by physicians , the HPV test results of self-collected samples, and the results of Pap smear and histopathological diagnosis at the same time . Taking the most serious pathological diagnosis as the standard, calculate :
  1. the sensitivity, specificity, positive predictive value and negative predictive value of cervical lesions based on the HPV test results of the samples taken by doctors
  2. the sensitivity, specificity, positive predictive value and negative predictive value of cervical lesions based on the test results of self- collected samples
- G. Use the subject questionnaire in the case report form to collect the survey data of the subject's self- test satisfaction survey, and conduct related evaluations.

### **Procedures for incorporating all data into the analysis**

the Investigator (Investigator ) , the test personnel are responsible for data collection and file management. All original documents and inspection reports must be reviewed by the research team and data entry personnel for correctness and completeness. Unexpected events and adverse events must be reviewed by the investigator or designee. The designated institution (Chang Gung Hospital Clinical Trial Center Biostatistics Group) is responsible for data management, confirmation, statistical analysis and output reports, and uses the data analysis software SAS for data collection and analysis.

### **In multi-center clinical trials, the minimum and maximum number of subjects included in each trial institution**

- A. This trial adopts a competitive type of case acceptance, and the case will stop after the expected number of trial subjects is included.
- B. each test institution will allocate 10 test work bags that meet the conditions of the subjects . According to the acceptance speed of each test institution, when the test work bags are estimated to be used up, an application should be submitted to the test commissioner to supplement the next batch of test work bags to make the test run smoothly.
- C. Based on the above, in this trial, each trial institution will include a minimum of 50 subjects, but there is no standard for the maximum number of subjects.

Except for the analysis of the main evaluation indicators and secondary evaluation indicators in this trial, the rest of the data analysis is exploratory analysis.

**All data included in the output table of the analysis**

Figure 1. Test flow chart

[figure not shown]

Table 1 Basic information of subjects

Characteristics	Total		Group 1		Group 2		Group 3		Group 4		Group 5	
	N	(N=)	N	(N=)	N	(N=)	N	(N=)	N	(N=)	N	(N=)
Age (year)												
Mean ± SD												
Median, range												
Colposcopy												
Yes												
No												
Finding												
Normal												
Punctuation												
Mosaicism												
Atypical vessels												
Condyloma accuminata												
Leukoplakia												
Invasive carcinoma suspected												
Others												
Past history of cervical histology*												
CIN1												
CIN2												
CIN3												
LSIL												
HSIL												

Squamous cell carcinoma

Adenocarcinoma

Others

None

Menopausal

No

Yes

Histological results

SM-C-

SM+

atypical

CIN1

CIN2

CIN3

SCC

AIS

Adca

clearCC

No biopsy taken

---

\*Histological diagnosis preferred

ASCUS, atypical squamous cell of undetermined significance

ASCH, atypical squamous cells favor high-grade squamous intraepithelial lesion

CIN, cervical intraepithelial neoplasia

HSIL, high-grade squamous intraepithelial lesion

LSIL, low-grade squamous intraepithelial lesion

Table 2 Smear examination results before inclusion in the trial (90 days ago)

Cytology	Total		Group 1		Group 2		Group 3		Group 4		Group 5	
	N	%	N	%	N	%	N	%	N	%	N	%
No Pap smear taken												
Within normal limit												
Reactive changes: Inflammation, repair, radiation, and others												
Atrophy with inflammation												
Atypical squamous cells (ASCUS)												
Atypical glandular cells												
Mild dysplasia (CIN1) with koilocytes												
Mild dysplasia (CIN1) without koilocytes												
Moderate dysplasia (CIN2)												
Severe dysplasia (CIN3)												
Carcinoma in situ (CIN3)												
Squamous cell carcinoma												
Adenocarcinoma												
Other malignant neoplasm												
Other												
Atypical glandular cells favor neoplasm												
Atypical squamous cells cannot exclude HSIL												
Dysplasia cannot exclude HSIL												
Endocervical adenocarcinoma in situ												

Table 3 Smear examination results when included in the trial (within 90 days)

Cytology	Total		Group 1		Group 2		Group 3		Group 4		Group 5	
	N	%	N	%	N	%	N	%	N	%	N	%
No Pap smear taken												
Within normal limit												
Reactive changes: Inflammation, repair, radiation, and others												
Atrophy with inflammation												
Atypical squamous cells (ASCUS)												
Atypical glandular cells												
Mild dysplasia (CIN1) with koilocytes												
Mild dysplasia (CIN1) without koilocytes												
Moderate dysplasia (CIN2)												
Severe dysplasia (CIN3)												
Carcinoma in situ (CIN3)												
Squamous cell carcinoma												
Adenocarcinoma												
Other malignant neoplasm												
Other												
Atypical glandular cells favor neoplasm												
Atypical squamous cells cannot exclude HSIL												
Dysplasia cannot exclude HSIL												
Endocervical adenocarcinoma in situ												

Table 4 Consistency of high-risk HPV detection in all cases

Physician-collected		Kappa statistic (95% CI)	p value	Overall Agreement
Self-collected	Positive	Negative		
Positive				
Negative				

High-risk HPV types include 16, 18, 31, 33, 35, 39, 45, 51, 52, 56, 58, 59, 66, 68 and other 14 types. The definition of consistency is as follows: high-risk HPV test results are concordant (concordant), the test results of the subject's physician -collected sample and self- collected sample both have any of the above-mentioned high-risk HPV (high-risk HPV positive) or both have no high-risk HPV (high-risk HPV negative); high-risk HPV test results are inconsistent (discordant), the test results of the subject's doctor-collected sample and self-collected sample, one does not have any high-risk HPV, and the other has any of the above- mentioned high -risk types .

Table 5 Consistency of high-risk HPV types detected in each group

Self-collected	Physician-collected		Kappa statistic (95% CI)	p value	Overall Agreement
	Positive	Negative			
Group 1					
Positive					
Negative					
Group 2					
Positive					
Negative					
Group 3					
Positive					
Negative					
Group 4					
Positive					
Negative					
Group 5					
Positive					
Negative					

High-risk HPV types include 16, 18, 31, 33, 35, 39, 45, 51, 52, 56, 58, 59, 66, 68 and other 14 types. The definition of consistency is as follows: high-risk HPV test results are concordant (concordant), the test results of the subject's physician -collected sample and self- collected sample both have any of the above-mentioned high-risk HPV (high-risk HPV positive) or both have no high-risk HPV (high-risk HPV negative); high-risk HPV test results are inconsistent (discordant), the test results of the subject's doctor-collected sample and self-collected sample, one does not have any high-risk HPV, and the other has any of the above- mentioned high -risk types .

Table 6 Consistency of detecting any type of virus in all cases

Self-collected	Physician-collected		Kappa statistic (95% CI)	p value	Overall Agreement
	Positive	Negative			
Positive					
Negative					

27 HPV types: HPV6, 11, 16, 18, 31, 33, 35, 39, 45, 51, 52, 53, 54, 56, 58, 59, 61, 62, 66, 68, 69, 70, 72, 73, 81, 82, 84. Consistency is defined as follows: HPV test results are concordant, the test results of the subject's physician-collected sample and self-collected sample both have any of the above-mentioned HPV types (HPV-positive) or neither of the above-mentioned types (HPV-negative); HPV test results are inconsistent (discordant), the test results of the subject's physician-collected sample and self-collected sample, one does not have any of the above-mentioned HPV types, and the other has any of the above-mentioned HPV types.

Table 7 Consistency of HPV16, HPV18, HPV16 or 18, non-16/18 high-risk HPV and low-risk HPV detected in all cases

Self-collected	Physician-collected		Kappa statistic (95% CI)	p value	Overall Agreement
	Positive	Negative			
HPV 16 a					
Positive					
Negative					
HPV 18 b					
Positive					
Negative					
HPV 16/18 c					
Positive					
Negative					
hrHPV non-16/18 d					
Positive					
Negative					
Non-hrHPV e					
Positive					
Negative					

aHPV 16: HPV 16 present only and/or co-infections with other types; bHPV 18: HPV 18 present only and/or co-infections with other types; cHPV 16/18: HPV16 and/or HPV18 present and/ or co-infections with other types; dHPV31, 33, 35, 39, 45, 51, 52, 56, 58, 59, 66, and 68 excluding HPV16 and HPV18 ; eHPV 6, 11, 53, 54, 61, 62, 69, 70, 72, 73, 81, 82 and 84 excluding HPV16, 31, 33, 35, 39, 45, 51, 52, 56, 58, 59, 66, and 68.

Table 8 Distribution of all measurable HPV types in medical samples and self- collected samples of each group

HPV	Total	Group 1	Group 2	Group 3	Group 4	Group 5
	( N=)	( N=)	( N=)	( N=)	( N=)	( N=)
6	Physician	Self	Physician	Self	Physician	Self
11						
16						
18						
31						
33						
35						
39						
45						
51						
52						
53						
54						
56						
58						
59						
61						
62						
66						
68						
69						
70						
72						
73						
81						
82						
84						
Negative						

Figure 2. Distribution of HPV types on physician-collected and self-collected specimens

Figure 3. Distribution of HPV types in Physician-collected and Self-collected specimens without precancerous lesions or cervical cancer (N = )

Figure 4. The distribution of HPV types on physician-collected and self-collected specimens of participants with cervical intraepithelial neoplasia grade 1

Figure 5. The distribution of HPV types on physician-collected and self-collected specimens of participants with cervical intraepithelial neoplasia grade 2 (N = )

Figure 6. The distribution of HPV types on physician-collected and self-collected specimens of participants with cervical intraepithelial neoplasia grade 3 (N = )

Table 9 Sensitivity, specificity, PPV and NPV between medically collected and self- collected HPV test results and cervical histopathology

cervical histopathology	self- collected specimen		Physician check		Relative accuracy	
	n/N	(95% CI)	n/N	(95% CI)	(95% CI)	p value
CIN1+						
Sensitivity						
Specificity						
Positive predictive value						
Negative predictive value						
CIN2+						
Sensitivity						
Specificity						
Positive predictive value						
Negative predictive value						
CIN3+						
Sensitivity						
Specificity						
Positive predictive value						
Negative predictive value						

\*No histological diagnosis is calculated as Negative

Table 10 Analysis of Satisfaction Questionnaires Included in Total Cases (N = , ITT)

satisfaction survey	very low		Low		high		very high	
	N	%	N	%	N	%	N	%
1. Do you like the appearance design of this product?								
2. Do you find it easy to use this product ?								
3. Using self -testing to screen for HPV will increase your willingness to do HPV screening regularly ?								
4. Would you like to use this product again next time ?								
5. Would you like to recommend relatives and friends to use this product ?								
6. May I ask you, is the process of putting this product into the vagina for sampling easy ?								
7. Do you think the process of using this product for inspection is safe ?								
8. Do you feel comfortable after using this product ?								
9. Is the instruction manual of this product easy to understand ?								

Table 11 Self -sampling Illustrative Video Questionnaire (N = , ITT)

Self- Sampling Instructions Video Questionnaire	yes		no	
	N	%	N	%
1. Can I use the self -testing stick to take samples during the menstrual period? sampling stick to sample when there is a lot of mucus secretion during the ovulation period?				

Table 12 Adverse events related to experimental medical materials (N = , ITT)

Patient	Adverse Events	Grade	Onset Time	Duration Related SAE

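### Do footnotes d and e of SAP Table 7 leave two kappas undefined because HPV18 is missing and co-infection is not addressed?

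*SAP*

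**What the plan says.** The SAP's primary evaluation indicators list HPV16, 18, 31, 33, 35, 39, 45, 51, 52, 56, 58, 59, 66 and 68 and state that these "14 types are high-risk cancer-causing types".

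Table 7 is titled "Consistency of HPV16, HPV18, HPV16 or 18, non-16/18 high-risk HPV and low-risk HPV detected in all cases". Its footnotes differ in form:

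- Footnote a, for HPV16, reads "HPV 16 present only and/or co-infections with other types". Footnotes b and c treat HPV18 and HPV16/18 in the same way, so co-infected specimens count as positive.
- Footnote d lists the other 12 high-risk types, then adds "excluding HPV16 and HPV18".
- Footnote e lists 13 low-risk types and ends "84 excluding HPV16, 31, 33, 35, 39, 45, 51, 52, 56, 58, 59, 66, and 68".

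Footnotes d and e say nothing about co-infection. The body text, item F of the statistical design section, covers single types only: "For each HPV type ( type-specific) , the consistency between the test results" is to be assessed by kappa or related tests. The note to Table 6 defines disagreement by presence: "one does not have any of the above-mentioned HPV types, and the other has any of the above-mentioned HPV types". The SAP also states that, outside the primary and secondary indicators, "the rest of the data analysis is exploratory analysis".

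**The concern.** The types listed in d and e do not overlap the types they exclude. If the exclusion describes only the list, it is redundant, so a reader may take it as a rule about specimens. The SAP would then have to say whether a co-infected specimen is scored negative or its pair leaves the 2x2 table, and it says neither.

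Under the scored-negative rule the gap at HPV18 has an effect: a specimen with HPV18 and HPV6 is Non-hrHPV positive, while one with HPV16 and HPV6 is not. Agreement on one class would also depend on another class. HPV16+52 against HPV52 would be discordant in row d although both specimens carry HPV52. HPV16+52 against HPV16 would be concordant and hide a real HPV52 mismatch.

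At stake is whether two programmers would report the same kappa, or the same denominator, for these two rows.

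**Working it through.** **Type lists.** The high-risk panel has 14 types and footnote e's exclusion list has 13; the difference is HPV18 alone. Footnote e's 13 low-risk types plus the 14 high-risk types give 14 + 13 = 27, the panel printed under Table 6. Footnote d's 12 types plus HPV16 and HPV18 give the 14. The intended partition can be recovered without doubt.

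**Which reading the SAP supports.**

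- *Presence (any listed type makes the specimen positive).* The row labels name classes of types. Every definition of agreement that the SAP writes out (primary indicators, item F, notes to Tables 4 to 6) works by presence in each specimen. Footnotes d and e mention no specimen, pair or removal.
- *Scored negative.* The support is the redundancy of the exclusion and the contrast with footnotes a to c.
- *Pair removed.* This conflicts with a title that covers all cases.

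Presence is the best supported. Under it the exclusion removes nothing, and the missing HPV18 changes no count.

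**Size under the other readings.** The documents give overall positivity: 0.10×0.10 + 0.15×0.70 + 0.20×0.50 + 0.20×0.70 + 0.35×0.90 = 0.67, which reproduces the SAP's figure. They give no co-infection, low-risk or HPV18 rates. Assumed: independence, equal margins, own-type and high-risk kappa 0.72, low-risk carriage f of 10 to 30%, HPV18 2 to 5%.

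For prevalence p and kappa κ, discordance is D = 2p(1−p)(1−κ), both-positive is p − D/2 and both-negative is 1 − p − D/2.

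Row e, scored negative, f = 0.20, all 14 types excluded:

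- Low-risk: D = 0.28×2×0.20×0.80 = 0.0896; both-positive 0.1552.
- High-risk: D = 0.28×2×0.67×0.33 = 0.1238; both-negative 0.2681.
- Row margin 0.20×0.33 = 0.066; both-positive 0.1552×0.2681 = 0.0416; D = 2(0.066 − 0.0416) = 0.0488.
- κ = 1 − 0.0488/(2×0.066×0.934) = 0.604, against 0.72 by presence.

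With the printed 13 types, positivity is 1 − 0.33/0.98 = 0.663 (HPV18 at 2%) or 1 − 0.33/0.95 = 0.653 (at 5%). Over f = 10 to 30%, κ is then 0.60 to 0.62, a loss of 0.10 to 0.12.

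HPV18 omission alone, f = 0.20: 0.605 as printed against 0.602 with HPV18 added (2%), and 0.607 against 0.599 (5%). The differences are 0.003 and 0.008. Building the 14-type class this way implies a high-risk kappa of 0.716 or 0.710, so these values lie slightly below 0.604.

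Row e, pair removed: 1,200×0.9 = 1,080 valid pairs; 1,080×0.2681 = 290 remain with 14 types, and 296 to 307 with 13. Kappa stays at 0.72 under independence.

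Row d, scored negative, with listed types at 50% (kappa 0.72) and HPV16/18 at 25% (kappa 0.80): margin 0.375; both-positive 0.43×0.7125 = 0.306; D = 0.137; κ = 1 − 0.137/(2×0.375×0.625) = 0.707. With listed types at 30 to 50% and HPV16/18 at 15 to 35%, the loss is 0.01 to 0.03 (HPV16/18 kappa 0.80) or 0.03 to 0.06 (kappa 0.72).

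**Second model, by simulation.** Assumed true prevalence: HPV16 20%, HPV18 6%, other high-risk 52%, low-risk 20%. Detection and false-positive rates ran from 0.85/0.05 to 0.95/0.02. Scoring co-infection as negative lowers row d by 0.05 to 0.09 and row e (13 types) by 0.07 to 0.13. The HPV18 omission then moves row e by 0.02 to 0.03.

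**The case for a change.** The best case for a change is that the footnotes switch wording partway through one set. A careful programmer could take the switch as deliberate and program a hierarchical class. A row e loss of about 0.1 exceeds the 0.06 between the SAP's null kappa of 0.66 and its assumed 0.72. The trial is meant to support a device registration, and a rule chosen after unblinding is open to data-driven choice. The correction would cost two footnotes and no data.

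Much of this stands. HPV18 is missing, footnotes d and e are silent on co-infection, and the two kappas are not uniquely defined by the footnotes alone. They are not undefined, however: each reading gives a computable kappa, and the rest of the SAP points to one of them. The comparison with 0.06 is one of scale only, since the stated hypothesis concerns any high-risk HPV and neither row is tested against 0.66. Removal of pairs would also show in the 2x2 counts that Table 7 prints. Choosing between presence-based and hierarchical rows is a legitimate trade-off, and both are used sensibly.

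**Conclusion.** The missing HPV18 is most likely a clerical slip in a shell-table footnote. The silence on co-infection is a gap that analysts would fill by presence, as the SAP does elsewhere. On that reading neither point alters a number.

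The losses of about 0.1 (row e) and 0.01 to 0.09 (row d), and the HPV18 effect of 0.003 to 0.03, arise only if co-infected specimens are scored negative. They also depend on assumed prevalences, independence and detection rates, and the two models differ several-fold on the HPV18 effect and on row d.

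The scope is two grouped rows that neither the primary nor the secondary indicators name, so they are best regarded as exploratory. Rewording the footnotes would change nothing that the trial does or concludes.
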